4.4 Screening and Enrollment Procedures

4.4.1 Eligibility review

Patients presenting with urinary stone disease will be screened for this study. Initial eligibility criteria for the study will be determined by the investigator based upon review of their medical history, presentation and diagnostic imaging. If the participant appears to meet the study criteria, then the investigator will explain the investigational treatment, provide information regarding the potential risks and benefits, explain the follow-up requirements and obtain written informed consent per the informed consent process.

4.4.2 Informed consent process

The investigator, or authorised designee, is responsible for obtaining written informed consent from each participant using the IRB/EC approved consent form prior to initiation of any study specific assessments or procedures.

Potential study participants will be given adequate time to review the consent form, ask questions, and consider their options before being asked to sign the form. Informed consent shall be obtained under circumstances that minimise the possibility of coercion or undue influence. The information that is given to the participant shall be in language understandable to the participant. The participant will not be led to believe that they are waiving their rights as a study participant or the liability of the sponsor or investigator.

Study participants will be informed that the sponsor and regulatory authorities will have access to personally identifying information for the purposes of monitoring data against source documentation. However, all data stored and presented by the sponsor will be de-identified. The participant will be asked to sign one copy of the informed consent form. The original, signed document remains at the investigational site and a copy (or second signed original) is given to the participant.

If new information regarding the investigational device becomes available and/or the clinical investigational plan (CIP) changes and the information can significantly affect a participant's future health and medical care, participants will be informed of the information and may be asked to sign a revised informed consent form.

Any modification to the study sample informed consent form made by the Investigational Site must be approved by the sponsor and the IRB/EC before use. Each Investigational Site will provide the sponsor with a copy of the EC approved consent forms.

4.4.3 Screening assessments

Refer to Section 6.1 for screening assessments.

4.4.4 Point of enrollment

Enrollment is defined as that time when the participant signs the informed consent form and is then eligible to begin screening assessments. Participants who fail to meet screening assessment requirements (see Section 6.1) will be counted as a screen failure and will not be treated with the ELS. Screen failures will be documented at the site on a screening log.

Each enrolled study participant will be assigned a unique participant identification number at the time of enrollment. This participant identification number will be retained throughout the study. Investigational site will keep a log that notes the participant's name and corresponding participant identification number. All electronic case report forms (eCRFs) will be tracked, evaluated, and stored using only the participant ID number. No personal identifying information will be included on the eCRFs.

4.5 Participant Withdrawal or Discontinuation

Study participants may withdraw from the study at any time at their request and may also be discontinued at the physician's discretion or for other event/s related to the participant's health or welfare, including study participants' non-compliance with pre-study requirements. Participation in the study will cease immediately if the study participant requests to be terminated from the study.

5. STUDY ENDPOINTS

5.1 Primary Endpoint

Treatment success: Proportion of study participants who are successfully treated following up to 2 ELS treatments [defined as absence of stones or with remaining fragments of less than 3 mm on the largest dimension by follow-up imaging through 30 day visit after last ELS procedure].

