	
During Procedure (up to 2 ELS treatments):
 
Cystoscopy with local anaesthesia and light or moderate sedation or light general anaesthesia (investigator's discretion), placement of ureteral catheter, periodic fluoroscopic and/or diagnostic ultrasound imaging (at investigator's discretion), intraluminal ureteral placement of ELS Acoustic Enhancer material and administration of acoustic energy. Multiple repetitions of ELS Acoustic Enhancer placement-insonation cycle will be performed
 
Follow-up:
 
1, 2, 3, 7 days (telephone follow-up): Assess pain and pain medications, evaluate for AEs
 
14 (\pm 4) days (on site exam): KUB X-ray and ultrasound; physical exam; assess pain and pain medications; urine culture; evaluate for AEs; Assess for eligibility for 2nd ELS Treatment (i.e. treated stone/fragment is \geq 3 mm and subject remains eligible per I/E criteria)
 
30 (\pm 4) days after last ELS procedure: CT scan (non-contrast) to evaluate stone status; physical exam; assess pain and pain medications; evaluate for AEs; serum creatinine; Assess for eligibility for 2nd ELS Treatment
 
Treatment 2 (if necessary): Repeat ELS treatment if subject meets eligibility criteria (i.e. treated stone/fragment is \geq 3 mm and subject remains eligible per I/E criteria). If performed, repeat Day 1, 2, 3, 7, 14 & 30 Follow-Up visits
 
90 (\pm 21) days: physical exam; serum creatinine; evaluate for AEs and record medications; renal-bladder ultrasound for safety assessment

Primary Endpoint	Treatment success: Proportion of study participants who, after up to 2 ELS treatments, have a complete absence of stones or with any residual fragments measuring less than 3 mm in the largest dimension as assessed by follow-up imaging through 30 day follow-up after last ELS procedure
Secondary Endpoints	
 • Proportion of participants with Serious Device and/or Serious Procedure-Related AEs from initial ELS Treatment through 30 days following last ELS treatment • Proportion of participants with Serious Device and/or Serious Procedure-Related AEs from initial ELS Treatment through 90 days following last ELS treatment • All AEs & SAEs from initial ELS Treatment through 30 days following last ELS treatment • All AEs & SAEs from initial ELS Treatment through 90 days following last ELS treatment • Participant satisfaction at 30 day follow-up following last ELS treatment

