Other Observations	
 • Pain scores will be assessed using a validated pain scale, summarized and tabulated by visit, including subgroups of

	
participants with pain versus no pain at baseline, and grouped by pain medication usage
 
 • Use and quantity of pain medication for managing stone-associated pain, including timing and type of medication, will be tabulated • The anaesthesia regimen used during ELS procedures (e.g. general/local) will be tabulated • Procedural data will be tabulated • Length of hospital stay will be tabulated • Stones and stone fragments recovered through post-ELS treatment urine straining will be characterized for chemical composition
Study Success Criteria	
The observed treatment success rate as defined in the proposed study will be assessed against a literature reference rate of 63.96% to evaluate similarity of the study outcomes to published performance. The relevant hypothesis test will be conducted by computing the 95% exact confidence interval on the study success rate. Note: this is a reference rate that was derived from the AUA Guidelines (2016) and is based upon treatment of stones less than or equal to 10 mm within the ureter by shockwave lithotripsy

GLOSSARY OF ABBREVIATIONS:

ABBREVIATION	TERM
AE	Adverse Event
ASA	American Society of Anaesthesiologists
ASADE	Anticipated Serious Adverse Device Effect
BMI	Body Mass Index
CIP	Clinical Investigation Plan
CIRF	Clinically Insignificant Remaining Fragments
CT	Computed Tomography
DMP	Data Management Plan
EC	Ethics Committee
eCRF	Electronic Case Report Form
ELS	Enhanced Lithotripsy System
SWL	Shock Wave Lithotripsy
IFU	Instructions for Use
IRB	Institutional Review Board
ISO	International Organization for Standardization
KUB	Kidney, ureter & bladder
PNL	Percutaneous Nephrolithotomy
SADE	Serious Adverse Device Effect
SAE	Serious Adverse Event
SWL	Shockwave Lithotripsy
TGA	Therapeutic Goods Administration
UADE	Unanticipated Adverse Device Effect
USADE	Unanticipated Serious Adverse Device Effect
URS	Ureteroscopy

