- Complete pain questionnaire (pain score).
- ELS Treatment eligibility will be assessed by the investigator. If the remaining stone size is 3 mm or more in any dimension, the participant is eligible for one additional ELS Procedure. Refer to Section 6.2.8.

6.2.6 30-day follow-up (30 +/- 4 days after each ELS procedure)

- Participants will undergo a low-dose non-contrast CT scan to assess ureter, stone (residual fragment) size, location and radiodensity (if stone/fragment present).
- Conduct an on-site follow-up after the last ELS treatment: 1) 30 days after first ELS treatment, if first treatment was successful, or 2) 30 days after second ELS treatment, if a second treatment was performed.
- Conduct focused physical exam
- Serum creatinine to assess renal function
- Document any reported AEs since last visit (see Adverse Events section below).
- Complete pain questionnaire (pain score) and document any pain medications
- ELS Treatment eligibility will be assessed by the investigator. If the remaining stone size is 3 mm or more in any dimension, the participant is eligible for one additional ELS Procedure. Refer to Section 6.2.8.

6.2.7 90-day follow-up (90 +/- 21 days after last ELS procedure)

Conduct an on-site follow-up after the last ELS treatment.

- Conduct focused physical exam
- Serum creatinine to assess renal function
- Perform diagnostic renal-bladder ultrasound to assess ureter.
- Document any reported AEs since last visit (see Adverse Events section below).
- Document concomitant medications

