7. RISKS AND BENEFITS

7.1 Potential Risks

The potential risks associated with the ELS procedure are expected to be similar or less than those of traditional SWL procedures used to treat urinary stones. Potential adverse events, which may be associated with the ELS and ELS Acoustic Enhancer material, and medications prescribed for use during these procedures include:

- Haematuria
- Pain or discomfort
- Skin redness where the treatment head is held against the body or from the belt that may be used to hold the treatment head in place
- Sensitivity/Tenderness over the treatment area
- Urinary blockage from stone fragmentation
- Bruising of tissue along the path of acoustic energy entering the body
- Urinary tract infection or inflammation
- Fever
- Mild cardiac arrhythmia could result from acoustic energy
- Bruising or damage to the kidneys, or tissue near the kidneys
- Allergic or anaphylactic reaction.
- Differential pressure risks include pressure from backflow of urine in the urinary tract system, and in rare cases rupture in the urinary tract

The procedure is also associated with potential anesthesia risks:

- Reaction to anesthesia
- Bleeding at anesthesia site
- As with any procedure performed with sedation or anaesthesia, there is risk associated that includes heart attack, stroke, and even death.

As with shock wave lithotripsy for urinary stones, the following adverse events may occur while being treated with ELS:

- Common (estimated as greater than 20% of patients)¹
 - There may be mild bleeding (including blood in the urine) or irritation from the ELS procedure. In rare cases, transfusion may be required to address bleeding.
 - There could be pain associated with the ELS sound wave energy effects and resulting stone fragments, with placement and movement of instruments in the urinary tract, or from other aspects of the procedure.
 - There could be skin redness around where the treatment head was held during the procedure, or irritation or bruising of the skin from the belt used to hold the treatment head in place during the procedure.

¹ Estimated occurrence rates are referenced from FDA, Center for Devices and Radiological Health: Guidance for the Content of Premarket Notifications (510(k)s) for Extracorporeal Shock Wave Lithotripters Indicated for the Fragmentation of Kidney and Ureteral Calculi (August 9, 2000)

- Occasional (estimated as 1-20% of patients)

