 - As with any intervention to fragment kidney stones, urinary blockage with a need for alternative treatment may occur. Blockage could be due to stone fragments after the ELS procedure. Also, the stone may be incompletely fragmented, causing urinary tract blockage. – In the case of urinary blockage, an ureteral stent or a tube in the kidney (i.e. nephrostomy tube) may be needed in order to properly relieve the obstruction.
 - There may be bruising of tissue along the path of acoustic energy entering the body through the skin of the lower back.
 - The urinary tract could become infected, or existing urinary tract infection could become worse.
 - There is a possibility of fever.
 - There may be nausea or vomiting associated with administration of anesthesia or other aspects of the ELS procedure.
- Rare (estimated as less than 1% of patients).
 - In rare instances, there could be bruising or damage to the kidneys or tissue near the kidneys, resulting in pain and requiring further treatment. In very rare instances, this could require kidney removal.
 - In rare instances, the acoustic energy could result in mild cardiac arrhythmia (irregular heartbeats).

As with other treatments for urinary stones, sloughed tissue found in or on urinary stones may be released as a result of ELS treatment. In addition, malfunction of the equipment is a possibility and the procedure may need to be rescheduled.

Possible adverse events associated with the placement of the ELS Acoustic Enhancer material in the urinary tract during treatment with the ELS:

The major risk associated with ELS Acoustic Enhancer material is an allergic (less than 1 in a 10,000 patients) or anaphylactic reaction (less than 1 in 20,000 patients). The doctor will be there to address these complications in the unlikely chance that they occur.

The placement of the ELS Acoustic Enhancer follows a standard procedure used in a common diagnostic procedure (retrograde pyelogram). As such, there is a very low risk of adverse events associated with the differential pressures in the urinary tract arising during ELS Acoustic Enhancer placement. Differential pressure risks include pressure from backflow of urine in the urinary tract system, and in rare cases rupture in the urinary tract.

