11.3 Primary Endpoint

The study’s primary endpoint is treatment success, which is the proportion of study participants who are successfully treated following up to 2 ELS treatments. This is defined as absence of stones or with remaining fragments of less than 3 mm on the largest dimension by follow-up imaging through 30 day visit after last ELS procedure. If ELS Treatment was performed on two stones in one participant, both stones/fragments need to meet the endpoint to be counted as a success.

The study will test the statistical hypothesis that the treatment success rate is not inferior to the performance goal defined using published AUA treatment guidance (64%). Formally, the null and alternative hypotheses are as follows:

$$H_0: p < PG$$

$$H_A: p > PG$$

where p is the success rate observed in the prospective study outcomes and PG is the performance goal. The PG in turn is computed as:

$$PG = r - p - \Delta,$$

where r is the reference rate, p is a correction for differences in treatment success definitions and Δ is the statistical testing margin. These values are further defined as follows:

- $r = 64\% = 0.64$ is the reference rate derived from AUA guidance [13]
- $p = 4\% = 0.04$ is a correction factor for the difference between the definition of treatment success in the literature reference and the definition in the study protocol. Specifically, the reference rate is measured after any number of treatments, while the investigational protocol permits at most two treatments before treatment effectiveness is measured.
- $\Delta = 10\% = 0.10$ is the statistical testing margin for comparison.

Hence $PG = r - p - \Delta = 64\% - 4\% - 10\% = 50\% = 0.50$ in the primary endpoint hypothesis testing. The hypothesis test will be performed by comparing the observed success rate to the PG via exact binomial methods, where a lower two-sided 95% exact confidence bound exceeding the PG will constitute rejection of the null hypothesis.

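### The primary endpoint scores success by residual size alone, so a participant drained for fragment obstruction after ELS can count as a success; a pre-specified supplementary analysis should show the effect.

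*Combined protocol and SAP*

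**What the plan says.** The primary endpoint is worded in three places, all by size. Section 5.1 has "absence of stones or with remaining fragments of less than 3 mm on the largest dimension by follow-up imaging". The synopsis counts participants who "have a complete absence of stones or with any residual fragments measuring less than 3 mm in the largest dimension as assessed by follow-up imaging". Section 11.3 repeats the size criterion and adds one scoring rule, for participants with two treated stones: "both stones/fragments need to meet the endpoint to be counted as a success".

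Section 7.1 anticipates obstruction by the products of treatment: "Blockage could be due to stone fragments after the ELS procedure". It adds that "an ureteral stent or a tube in the kidney (i.e. nephrostomy tube) may be needed in order to properly relieve the obstruction". The item stands under the heading "Occasional (estimated as 1-20% of patients", a class whose footnote traces the rates to regulatory guidance on shock wave lithotripters.

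Section 6.4 says that interventions other than ELS on the selected stone are entered on an eCRF and assessed for adverse events. It gives no rule for how they score on the primary endpoint. The per-protocol definition (11.1) and the missing-data section (11.5) give none either. Under Section 6.2.6 the 30-day visit includes a "low-dose non-contrast CT scan to assess ureter, stone (residual fragment) size, location and radiodensity", but the endpoint uses only the size finding. Adverse events are secondary endpoints (5.2) and are reported descriptively (11.4).

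**The concern.** The endpoint asks what is left on imaging, not how the participant got there. Take a participant whose ureter is blocked by fragments after ELS, who has a stent or nephrostomy placed, and whose imaging then shows nothing of 3 mm or more. Every stated condition for success is met. The same holds if a different stone procedure under 6.4 clears the treated stone before the 30-day CT.

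Section 11.3 contains the only hypothesis test, and Section 2.2 says the data will support premarket applications. The adverse event tables will show these participants, but nothing in those tables can alter the tested success rate. A reader of the headline rate could not tell how many successes needed drainage or another procedure. With no rule set in advance, any later decision to count them as failures would be made with the results in view, when one participant may decide the outcome.

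**Working it through.** **Inputs.** From Sections 11.3 and 11.6: n = 58 evaluable; performance goal (PG) 0.50; assumed ELS success 0.68; pass if the lower limit of the two-sided 95% exact interval exceeds 0.50; stated minimum pass 37/58. The shares of affected participants below are assumptions, because the documents give no rate for this event.

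**1. The plan's own rule.** The exact (Clopper-Pearson) lower limit for x successes in n is the 2.5% quantile of Beta(x, n − x + 1).
- 37/58 = 63.8%: lower limit 0.5012 (the plan states 0.502; the difference does not matter).
- 36/58 = 62.1%: lower limit 0.4837.

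So 37 is the correct minimum. With X ~ Binomial(58, p), P(X ≥ 37) is 0.0240 at p = 0.50 and 0.7975 at p = 0.68. The design reproduces, with about 80% power and a one-sided error of 2.4%.

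**2. Reclassifying individual participants.**
- From 37/58, one reclassified gives 36/58, lower limit 0.484: a pass becomes a fail.
- From 39/58 (67.2%, about the planned rate), two reclassified gives 37/58 (0.501, still a pass) and three gives 36/58 (0.484, a fail).

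**3. Chance of passing when success without such events is exactly 50%.** The answer depends on how the affected share is expressed.

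(a) A share q of size-based successes is affected. The size-only rate is then 0.50/(1 − q).

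| q | Size-only rate | P(X ≥ 37) |
|---|---|---|
| 0 | 0.500 | 2.4% |
| 5% | 0.50/0.95 = 0.526 | 5.7% |
| 10% | 0.50/0.90 = 0.556 | 12.9% |

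(b) A further d percentage points of all participants are affected. The size-only rate is then 0.50 + d.

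| d | Size-only rate | P(X ≥ 37) |
|---|---|---|
| 5 points | 0.55 | 11.2% |
| 10 points | 0.60 | 32.7% |

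Reading (b) is the heavier one: 5/55 = 9% and 10/60 = 17% of all successes would be affected.

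**4. Power of an analysis that counts these participants as failures.** Start from a size-only rate of 0.68 and reclassify a share q of successes, so that p = 0.68(1 − q).
- q = 5%: p = 0.646, power 61%.
- q = 10%: p = 0.612, power 40%.

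**The case against.** The strongest reply is that this is a design choice. The plan separates performance, measured by stone status, from safety. Blockage is a listed risk, adverse events are collected at every follow-up contact, Section 8.1.4 makes many such events serious, and Section 11.4 promises tables and a line listing. The participants would be visible. That stands, and it is why the size-only definition is not an error. It does not answer the point that descriptive tables cannot change the tested result.

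Changing the primary definition would also have a price. The PG is built from a reference rate and a correction for differences in how success is defined (11.3). New failure conditions would mean rechecking the correction, the PG, the 68% assumption and the sample size. Scoring obstruction on CT would need a grading criterion that the plan lacks. These objections stand against redefining the primary, but not against a supplementary analysis.

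Four stronger readings are tempting, and the documents do not support them.
- A reader might infer that obstruction by small fragments is the device's main failure mode. Nothing says so. Residual stone of 3 mm or more is what triggers retreatment, and Section 7.1 also attributes blockage to incomplete fragmentation. Blocking pieces of 3 mm or more that persist already fail the endpoint.
- A reader might infer that such participants end worse off than at baseline. The documents do not show this. Ureteral stones can themselves obstruct, and the screening CT items in 6.1 do not include baseline obstruction.
- A reader might apply 1-20% to 58 participants as an expected count. The class is generic, covers several kinds of event and comes from guidance on another type of device. It is not an ELS rate, still less a rate for pieces under 3 mm.
- A reader might take the glossary entry "Clinically Insignificant Remaining Fragments" as a criterion that was dropped. In the text supplied the term appears only in the glossary, which does not show that.

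Section 11.7 defers further detail to a separate analysis plan. It may hold a rule, but the text supplied does not.

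**Conclusion.** The point holds in limited form. As written, a participant who needed a stent or nephrostomy for fragment obstruction, or another non-ELS procedure on the treated stone, can be scored a success, and no section supplied says otherwise. This follows from a size-only definition with no failure rule; the plan does not state it in words.

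The direction is certain: against a rule that fails these participants, the size-only rule can only raise the number of successes. The size is not known. The figures rest on assumed shares of 5% or 10%, on 58 evaluable participants and on a true rate of exactly 50% without such events. They run from 5.7% to 32.7% according to how the share is expressed, so neither end should be quoted alone. That one participant can reverse a result at 37/58 is true of any scoring rule at its boundary. It shows how thin a minimum pass would be, not how likely it is.

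This is a worthwhile, low-cost improvement to the plan, not a defect that invalidates the primary test.

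**What to change.** Keep the size-only primary, so that it stays comparable with the reference rate and the PG. In Section 11.3, pre-specify one supplementary analysis using the same exact 95% lower bound against 0.50, reported beside the primary. In it, score as failures all participants who, before the Day-30 assessment after their last ELS procedure, had either:
- a stent or nephrostomy placed to relieve fragment obstruction after ELS; or
- another non-ELS intervention on the treated stone, as recorded under Section 6.4.

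State that this analysis is supportive and does not replace the primary decision, and carry the rule into the separate analysis plan.

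Cost: one extra analysis, with no new visits or imaging. The interventions already go on an eCRF; the sponsor should confirm that the form captures type, date and reason, including drainage procedures. The supplementary success rate may be lower than the primary, and its power is lower too: about 61% if 5% of successes are reclassified from 68%. A supplementary lower limit below 0.50 would therefore not by itself show poor performance, and the text should say so in advance.
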